### 3) Objectives

We hypothesize that apneic oxygenation via nasal cannula during airway placement improves oxygen saturation in pediatric patients. Patients who receive this treatment will be compared to patients managed under the current standard of care, which does not include apneic oxygenation during anesthetic induction and airway management.

The primary outcome is the elapsed time between anesthetic induction and pulse oximetry (SPO2) falling to 95%, if it happens at all.

The secondary outcomes are as follows:

- whether the 95% threshold is met at all
- whether intervention by attending or temporary mask ventilation is required
- whether pulse oximetry falls to 90%
- the lowest observed pulse oximetry during airway placement

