## 6) Number of Subjects (Recruitment Target)

A sample size estimate based on prior studies of apneic oxygenation in adults indicates that approximately 400 subjects would be appropriate for this study, 200 in the baseline group without nasal cannula adjunct and 200 patients with implementation of nasal cannula adjunct during the peri-intubation period.

A power analysis (based on formulae in *Statistics in Medicine* 1982; 1:121-9) indicated that if the baseline rate of reaching 95% SPO2 is 15% of patients and this procedure reduces that rate by half, 80% power at  $\alpha=0.05$  is reached for a one-tailed logrank test with a total of 371 patients. Rounding up to 400 patients to accommodate incomplete datasheets would provide power of 94%.

Based on enrollment rate to date, we estimate that enrollment of 400 patients will take approximately one year. Because the planned evaluation of routine use of nasal cannula adjunct oxygenation is occurring independent of enrollment counts to the baseline study condition, data

may be gathered on more than 200 patients in that group. In order to permit analysis without loss of power, we may need to enroll a higher total sample size in order to achieve an equal sample size in the group with the cannula. To accommodate this reality, we may enroll a maximum of 500 patients in the entire study.

This period will also permit education of all relevant providers and staff on the use of peri-intubation nasal cannula oxygenation.

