## 8) Study Timelines

- Duration of individual patient participation: Patients will participate from the time when they are brought into the OR preoperative suite and it is determined they will have an endotracheal tube (ET) or laryngeal mask airway (LMA) placed. The study observation period will end once the airway has been secured.
- The duration anticipated to enroll all study subjects will be sufficient time to enroll the target sample of patients.
- An interim analysis will be conducted halfway through enrollment of the with-cannula group.
- The estimated primary analysis will be done by December 2016.

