**14) Data Management**

Only study investigators will have access to study data. Study participants will be assigned a study number, and this number will be used in all data analyses. The data will be entered into an electronic database that will be stored on UNMHSC password-protected servers. The electronic data will only have study participant numbers and no identifiers that could link specific patients to the data. All data forms that bear identifiers will be securely destroyed (shredded) upon application to HRRC for study closure, so that only deidentified data remain when that application is made.

As noted above, data to be gathered include basic demographic data, data about the anesthetic induction procedure, and data about the patient's O2 saturation.

Routine demographic data will be analyzed with t-tests and Wilcoxon rank-sum tests, as appropriate depending on normality of data distributions. Categorical data will be analyzed with appropriate analyses, such as chi-square, Fisher's exact, risk ratio, and/or odds ratio.

The primary outcome of time to cross the 95% saturation threshold will be analyzed with Kaplan-Meier curves and survival analysis with "censoring" for cases in which the threshold was not crossed because of either successful intubation or intervention by the attending physician.

Secondary outcomes with continuous data (e.g. the lowest observed O2 saturation) will be analyzed with standard t-tests or Wilcoxon rank-sum tests, as appropriate depending on normality of data distributions. Secondary outcomes with binary data (e.g. whether intervention by the attending physician is required) will be analyzed with chi-square or Fisher's Exact tests as appropriate depending on cell counts.

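### Kaplan-Meier curves that censor at a secured airway do not estimate the share of children who desaturate; any absolute risk read from them is too large, so a cumulative incidence curve should be added

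*Combined protocol and SAP*

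**What the plan says.** Section 3 defines the primary outcome as the time from induction to SpO2 "falling to 95%, if it happens at all". It lists the yes/no version, whether a child ever reaches 95%, as a secondary outcome.

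Section 14 states that the primary outcome "will be analyzed with Kaplan-Meier curves and survival analysis". Censoring applies where the "threshold was not crossed because of either successful intubation or intervention by the attending physician". I take intubation there to include laryngeal mask placement, since section 11 allows either device. Section 14 gives binary secondary outcomes a chi-square or Fisher's exact test. It names no cumulative incidence or competing-event estimate, and no other estimator for the primary outcome.

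Section 8 adds: "The study observation period will end once the airway has been secured".

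Section 6 states the effect as a share of patients. The baseline rate of reaching 95% "is 15% of patients and this procedure reduces that rate by half", and the size is set "for a one-tailed logrank test with a total of 371 patients".

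**The concern.** Ordinary censoring means that the event may still happen, unobserved, after follow-up stops. A secured airway is different. It ends the apnoea under study, so within this study the event can no longer occur. It is a competing event, and the common one: on section 6's figures, 100 − 15 = 85% of baseline children and 100 − 7.5 = 92.5% of cannula children leave without reaching 95%.

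Kaplan-Meier redistributes the children who leave among those still at risk, as if they would have gone on to desaturate at the same rate. Readers ordinarily take one minus such a curve as the proportion with the event by each time. Here that reading would give a risk and a risk reduction larger than those that occurred. The main display of the primary outcome would also not agree with the crude proportion reported alongside it.

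**Working it through.** **Inputs from the documents.** 15% and 7.5% reach 95%; 200 children per group; one-sided alpha 0.05; 80% power; N = 371 (section 6). Censoring rule: section 14. End of observation: section 8. The documents give no distribution of placement or desaturation times, so every time distribution below is an assumption.

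**1. The plan's own figure.** Freedman's log-rank formula with hazard ratio 0.5 gives

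events = (1.645 + 0.842)² × ((1 + 0.5)/(1 − 0.5))² = 6.183 × 9 = 55.6.

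Dividing by 0.15 gives N = 371, an exact match. The 15% thus enters the sample size as a crude share of children who have the event before observation ends. (The 94% power stated for 400 patients is not reproduced: 400 × 0.15 = 60 events, z = √60/3 − 1.645 = 0.937, power 82.6%. That is a separate matter.)

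**2. Direction.** Let h1 be the hazard of reaching 95% and h2 the hazard of leaving without it.

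- One minus Kaplan-Meier: 1 − exp(−∫h1).
- Cumulative incidence: ∫ h1(u) · exp(−∫₀ᵘ(h1 + h2)) du.

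The second can never exceed the first. They agree only while nobody has left. If every airway were secured at one fixed time, the ratio before that time would be 1.

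**3. Simplest size: exponential times.** When a fraction q of baseline children has left the risk set for either reason, cumulative incidence is 0.15q and one minus Kaplan-Meier is 1 − (1 − q)^0.15. For q = 0.9 these are 13.5% and 1 − 0.1^0.15 = 29.2%, a ratio of 2.2.

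For the cannula group, set the leaving hazard to 1 in both groups. The desaturation hazards are then 0.15/0.85 = 0.1765 and 0.075/0.925 = 0.0811, and q = 0.9 is reached at 2.303/1.1765 = 1.957. At that time:

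- one minus Kaplan-Meier = 1 − exp(−0.0811 × 1.957) = 14.7%;
- cumulative incidence = 0.075 × (1 − exp(−1.0811 × 1.957)) = 6.6%.

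The differences are 29.2 − 14.7 = 14.5 points against 13.5 − 6.6 = 6.9 points, a ratio of 2.1.

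| Baseline children out of risk set | Cumulative incidence | 1 − KM | Ratio, share | Ratio, difference |
|---|---|---|---|---|
| 50% | 7.5% | 9.9% | 1.3 | 1.3 |
| 90% | 13.5% | 29.2% | 2.2 | 2.1 |
| 95% | 14.3% | 36.2% | 2.5 | 2.4 |
| 99% | 14.9% | 49.9% | 3.4 | 3.0 |

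**4. A more realistic placement time.** Assume lognormal placement times, median 60 s, sigma 0.5, and Weibull desaturation times with shape 1, 2 or 3, scaled so that the crude shares are 15% and 7.5%. Numerical integration gives, for the baseline group:

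| Time | Still at risk | Cumulative incidence | 1 − KM | Ratio |
|---|---|---|---|---|
| 60 s | 43–46% | 5–12% | 7–14% | 1.2–1.4 |
| 90 s | 16–17% | 10–14% | 20–23% | 1.4–2.2 |
| 120 s | 4–6% | 13–15% | 25–46% | 1.7–3.5 |
| 180 s | under 1% | 15% | 36–87% | 2.4–5.9 |

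The ratio for the between-group difference at 120 s is 1.7 to 3.3. Varying sigma from 0.3 to 0.7 widens the ratio for the share to about 1.1–1.5 at the median and 1.7–4 at twice the median.

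**5. The test.** In a simulation with exponential times and 200 per group, the one-sided log-rank test rejected in 4.6% of null trials and had 82% power. The last value of one minus Kaplan-Meier averaged 59.6% and 35.6%, against crude shares of 15.0% and 7.5%. The difference is (59.6 − 35.6)/(15.0 − 7.5) = 3.2 times too large, while the test behaves as it should.

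**The case against.** The case for leaving the plan alone has substance.

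- **No absolute risk is promised from the curve.** Correct: the documents do not say so. A reader might infer that the trial will report an inflated benefit, but that would be a misreading of the display, not a stated plan. What stands is that section 14 offers no other estimator for the primary outcome, and such curves are ordinarily read as event probabilities.
- **The crude share is already planned.** Correct. Because section 8 follows each child until the airway is secured, the crude share gives the final absolute risk. It does not give the share by a given time, and it does not label the curve.
- **Kaplan-Meier suits the physiological question.** The background in section 4 concerns prolonging the time to desaturation during apnoea. Censoring at placement is conventional for that hazard question. Cumulative incidence also depends on how fast airways are placed, which may differ between phases enrolled one after the other with learner operators. This stands, and it is why the curve should be supplemented and labelled rather than dropped.
- **The primary test is unaffected.** Correct. A reader might infer that the log-rank result or the sample size is invalidated by this censoring; neither is.

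**Conclusion.** The point holds as one about the absolute scale of the curve. With a secured airway censored, one minus Kaplan-Meier lies at or above the share of children who reach 95%. Once children have left the risk set, a risk or difference read from it is too large. The direction follows from the definitions and needs no assumption.

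The size does need assumptions. It is roughly 1.1 to 1.5 times near the median placement time, about 1.7 to 4 times at twice the median, and about 6 times where almost nobody remains at risk. A reader might take a single multiple, such as two- to threefold, as a property of the plan. The documents do not support that: they give no time distributions, and such a multiple fits only a late reading of the curve under particular assumed times.

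Nor should all of the 85% and 92.5% be counted as secured airways. Section 14 also censors at attending intervention and gives no split. Whether that second kind of censoring is informative is a separate question.

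**What to change.** In section 14, keep the log-rank test and the crude proportion as planned, and add:

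- *The share of children reaching SpO2 95% over time is estimated by the Aalen-Johansen cumulative incidence function, with airway secured as a competing event and attending intervention as a second competing event. The between-group difference is reported with a 95% CI at a prespecified time. The log-rank test compares cause-specific hazards.*
- Numbers at risk under every curve.
- Absolute risks taken only from the cumulative incidence or the crude proportions.
- A label on any Kaplan-Meier curve: time to desaturation had apnoea continued.

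Treating attending intervention as a second competing event is one option, but the plan must state some rule. If intervention stays censored, the cumulative incidence need not end at the crude share. For the two to agree, the binary outcome must also stop counting at the same point; section 8 follows children to a secured airway, while section 14 stops at intervention if that comes first.

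The cost is a paragraph and one standard routine. Section 11 already has the time to intubation or intervention recorded. The downsides are two quantities to explain instead of one, and a cumulative incidence that also reflects placement speed. Reporting placement times by phase would let readers judge the second.

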## 11) Study Methods

This is a prospective observational study. Prospectively-recorded data are necessary because data on the outcomes of interest are not available in the medical record.

Participants will be enrolled in the study once they have entered the pre-operative area and they are determined by the attending anesthesiologist to

that they are an eligible study participant. Participants enrolled in the first three months of the study will be assigned to the baseline condition as described below. Participants enrolled in the second phase of the study will be assigned to the with-cannula condition described below.

A patient sticker will be added to the data collection form. Basic demographic information and vitals will be recorded before premedication is administered as is standard at entry to the pre-operative area. Timing devices of the same make and model will be used consistently between all study cases.

For the **baseline group** of this observational study, all intubation procedures will be performed as per usual practice. Patients will receive premedication as determined by anesthesiologist/resident/midlevel, and the type and dose will be recorded.

Once patients are brought to the operating room suite and vital signs are being monitored, patients will be preoxygenated via mask per standard of care, with an expired oxygenation concentration minimum of 0.75. Vitals will be recorded at the moment prior to removal of the face mask at the end of the preoxygenation period. Anesthetic induction will then be performed with agents and dosages as per the provider's clinical judgment.

Airway management consisting of oral endotracheal intubation or laryngeal mask airway insertion will take place. As per usual practice, an attending physician who is expert in pediatric airway management will supervise the procedure and intervene before the patient experiences excessive oxygen desaturation. The lowest oxygen saturation and the time to either successful intubation or intervention by an attending physician will be recorded.

For the **with-cannula group**, all of the above steps will be maintained. The sole difference will be nasal cannula placement after induction. It will be set to deliver 5L of oxygen per minute.

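### The primary analysis has no single end of follow-up: read literally, crossings after attending takeover count as events, while taken-over children who do not cross are censored at takeover

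*Combined protocol and SAP*

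**What the plan says.** Four places in the combined protocol and SAP determine who is at risk, and until when, in the primary analysis.

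- **Section 3 (Objectives), the event.** The outcome is the time from induction to SpO2 "falling to 95%, if it happens at all". Nothing in this definition stops the clock when the attending takes over. The first secondary outcome is "whether the 95% threshold is met at all".
- **Section 8 (Study Timelines), the end of observation.** "The study observation period will end once the airway has been secured". A child is therefore still under observation between takeover and the secured airway.
- **Section 11 (Study Methods), the recorded time.** "The lowest oxygen saturation and the time to either successful intubation or intervention by an attending physician will be recorded".
- **Section 14 (Data Management), the censoring rule.** Censoring applies "for cases in which the threshold was not crossed because of either successful intubation or intervention by the attending physician". No censoring time is given, and nothing is said about a crossing that follows takeover.

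Section 3 also lists "whether intervention by attending or temporary mask ventilation is required" as a secondary outcome, so the study itself tests whether takeover differs between the groups.

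**The concern.** Kaplan-Meier and log-rank methods require that a child's membership of the risk set at a given time does not depend on what happens to that child later. The four statements, taken at face value, break this condition.

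Consider two children, both taken over at 40 s. One reaches 95% at 55 s, before the airway is secured. That child crossed, so the censoring sentence does not apply, and the child is an event at 55 s. The other never reaches 95%. That child is a non-crosser, and the only non-event time section 11 names for a takeover case is the takeover time, so the child is censored at 40 s. Among taken-over children, those still counted at risk after takeover are exactly those who will go on to have the event.

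This differs from the familiar worry that takeover is prompted by falling saturation. The hazard is inflated even if takeover is unrelated to saturation. If takeover is more common in one group, that group's hazard is inflated more, and the primary comparison can show a cannula effect that does not exist or hide one that does. The primary result can also stop the study at the interim analysis (section 9).

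**Working it through.** The plan gives no figure on this point: no takeover rate, placement time or takeover-to-secured interval. There is nothing to reproduce, so the size has to be shown over a range.

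**Inputs from the documents (section 6):** 200 children per group, one-tailed log-rank test at 0.05, about 15% of baseline children reaching 95%.

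**Assumptions:** time from induction to secured airway S is gamma with shape 4 and scale 15 s (mean 60 s). Crossing time is exponential with rate λ = 0.002905 per second. Takeover occurs with probability p at a uniformly random point of the attempt, is unrelated to saturation and does not change the crossing hazard. The cannula has no effect.

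**Step 1: inflation within one group.** The hazard estimate is events divided by time at risk. The literal rule keeps every crossing before securing but drops the post-takeover time of non-crossers.

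- Proportion crossing: 1 − (1 + 15λ)^−4 = 1 − 1/1.1860 = 0.157.
- True time at risk per child: 0.15685/0.002905 = 53.99 s.
- Time lost per child: p × ½ × E[S·exp(−λS)] = p × ½ × 60/(1 + 15λ)^5 = p × ½ × 60/1.2377 = p × 24.24 s.
- Inflation: k(p) = 53.99/(53.99 − 24.24p).

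This gives k(0.10) = 53.99/51.57 = 1.05, k(0.30) = 53.99/46.72 = 1.16 and k(0.50) = 53.99/41.87 = 1.29. A simulation of 2,000,000 children gave 1.046, 1.155 and 1.288. In it the Kaplan-Meier crossing probability at 60 s (true value 16.0%) rose to 16.7%, 18.3% and 20.3%.

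**Step 2: effect on the test.** The spurious hazard ratio is k(p cannula)/k(p baseline). With 400 × 0.157 ≈ 62.7 events, the log-rank statistic shifts by about ½√62.7 × ln(HR) = 3.96 × ln(HR). The rejection rate is then Φ(−1.645 − shift). For 30%/15%: HR = 1.072/1.156 = 0.928, shift = 3.96 × ln(0.928) = −0.297, and Φ(−1.348) = 8.9%.

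**Step 3: simulated trials** (15,000 per row; 4,000 for the last row), rejection rate at nominal 5%:

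| Takeover, baseline/cannula | HR, formula | Rejection, formula | Literal rule, simulated | All cut at takeover | All followed to securing |
|---|---|---|---|---|---|
| 30%/30% | 1.00 | 5.0% | 4.8% | 4.8% | 4.8% |
| 10%/5% | 0.98 | 6.0% | 6.2% | 5.1% | 5.1% |
| 20%/10% | 0.95 | 7.3% | 7.4% | 5.0% | 5.1% |
| 30%/15% | 0.93 | 8.9% | 9.5% | 5.2% | 5.2% |
| 50%/25% | 0.87 | 13.4% | 14.3% | 5.2% | 5.4% |
| 15%/30% | 1.08 | 2.6% | 2.3% | 4.7% | 5.4% |

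With a true hazard ratio of 0.5 and takeover of 15%/30%, power was 66% under the literal rule, 71% with all cut at takeover and 75% with all followed to securing.

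**Step 4: other assumptions.** A second set of simulations used lognormal placement times (median 60 s), a median of 15 or 30 s from takeover to securing, and a constant or rising hazard. The literal rule rejected 6.0–8.6% of the time at 20%/10%, 6.8–11.2% at 30%/15%, and 2–4% with the imbalance reversed. Either single cut-off gave 4.5–5.5%.

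**The case against.** The strongest reply is that the faulty rule is inferred and not written. Section 14 puts attending intervention beside intubation as something that ends the attempt, and section 11 records the time to whichever occurs. A sensible analyst may take this to mean that follow-up ends at the first of the two for everyone, and that rule holds its size. This stands: the firm finding is that the plan leaves the rule open. It does not settle the matter, because sections 3 and 8 keep the event and the observation running past takeover, and nothing says that later crossings are ignored.

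Second, a reader might infer that the log-rank test is biased whenever takeover occurs, even at random. That is not so: at 30%/30% the size is 4.8%. Unequal takeover frequency or timing is a necessary condition. It is plausible here because the groups are enrolled in successive periods (section 11), learners perform the intubations (section 4), and takeover is itself a secondary outcome. It is not established.

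Third, the size rests on assumed rates. With shorter post-takeover intervals (median 15–30 s), 10%/5% gives only 5.2–6.0%. At 20%/10% the literal rule and the takeover cut-off differ by about 1.5 to 3 baseline children in 200. This stands.

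Fourth, a reader might infer that following everyone to the secured airway is the only valid primary. The documents do not support that either. Attendings are to "intervene before the patient experiences excessive oxygen desaturation", so takeover may itself lower the later hazard. If it halves that hazard (assumed; takeover 30%/15%, median 30 s to securing), following everyone to securing rejects about 3% of the time. The choice between the two ends of follow-up is a choice of estimand.

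Last, the data collection form is a listed appendix that is not available here. It may already hold both times, so it cannot be said that taken-over children cannot be followed to securing.

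**Conclusion.** The concern holds in a conditional form. The plan does not state one end of follow-up for the primary outcome, and the literal combination of sections 3, 8, 11 and 14 makes follow-up depend on the later outcome. Under that reading the estimated hazard is inflated within each group, by about 5% at 10% takeover and 16% at 30%. The one-tailed test is biased against the group with more takeovers. At nominal 5%, false positives are about 6% at 10%/5% takeover (baseline/cannula), 7% at 20%/10% and 10% at 30%/15%. With 15%/30% the rate falls to about 2.5%, and real effects become harder to detect. With equal takeover the test keeps its size.

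These figures rest on assumed takeover rates and placement times, and on takeover that is random and leaves the hazard unchanged. The takeover cut-off, which section 14 can also be read to intend, removes this particular error. It would leave the primary omitting crossings that the first secondary outcome counts. That is not a contradiction, but it should be stated. Whether takeover prompted by falling saturation makes censoring at takeover informative is a separate question.

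**What to change.** **Section 14.** State one end of follow-up that applies to crossers and non-crossers alike and to both groups. Either:

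- attending takeover or secured airway, whichever comes first, with later crossings not counted in the primary; or
- secured airway, whoever places it, with every earlier crossing counted and non-crossers censored at securing.

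Report the other rule as a sensitivity analysis, and say which one the first secondary outcome follows.

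**Section 11 and the data form.** Record both the takeover time and the secured-airway time, if the form does not already do so. Section 11 says the outcome data are not in the medical record, so a time not written down may be lost.

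**Data already collected.** Baseline children were enrolled first. If their secured-airway times are missing for takeover cases, use the takeover cut-off as primary in both groups. Applying one rule to earlier cases and another to later ones would give the two groups different follow-up.

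**Cost.** A sentence or two in section 14, one extra recorded time and one extra analysis. The takeover cut-off discards a few events; following to securing brings the effect of attending rescue into the comparison. Neither option changes patient care.
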